### ***Study procedures***

#### **Informed consent procedure**

Eligible patients will be asked to take part in the study at the time the diagnosis and the suggested surgical therapy are discussed at the outpatient services (either high suspicion of a malignant ovarian tumour planned for exploratory laparotomy or high-risk endometrial cancer planned for staging laparotomy). The gynaecological oncologist will explain the outline of the study and gives the patient the information brochure. Of course it will be stressed that the patient remains free to withdraw at any time from protocol investigations without giving reasons and without prejudicing any further treatment. After admittance to the hospital (one day before surgery) the gynecologist who will perform the surgery, once more discusses the study and, when the patient agrees to take part in the study, obtain a written informed consent.

### **Surgical procedures**

#### *Patients with a high suspicion of a malignant ovarian tumour*

After making the median incision and opening the abdomen, before starting with removal of the enlarged and suspicious adnex, blue dye and the radioactive isotope will be injected in the ligamentum ovarii proprium (median side) and the ligamentum infundibulo-pelvicum (lateral side), close to the ovary and just below the peritoneum. Four syringes will be made containing 0.2 ml patent blue and 0.15 ml (20-MBq) radioactive isotope (99mTc-nanocolloid or Nanocoll®, GE Healthcare, Eindhoven, The Netherlands, see appendix for information leaflet) will be given. Mixing patent blue and radioactive isotope does not affects the quality of the two substances, nor does it give extra or different side effects for the patient [36]. The

99mTc-nanocolloid is prepared by trained laboratory staff on the nuclear lab in a sterile 'class A' Laminar Air Flow (LAF) hood. Afterwards patent blue is added and the syringe is mixed. This is done 30 minutes before the start of the surgery.

A 15-minute interval will be planned after injection. The exact time interval for detection of positive nodes is unclear. Common practice is to wait for 15 minutes, if in this time period the node is not detected, it is considered negative. In daily practice a wait of more than 15 minutes during surgery is not workable. At 5 and 10 minutes the radioactivity will be measured along the lymphatic tract to document whether or not perhaps sentinel node(s) can be identified at a shorter time-interval in future studies. A Geiger counter measures the radioactivity. The Geiger counter will be the same device in all surgeries.

After the 15 minutes time-interval the adnex will be removed and admitted to the pathologist for a frozen section. If the result is benign, no further actions will be performed in these patients. If the result is malignant, the sentinel node(s) will be identified either (once more) by the radioactive tracer and / or visually (blue dye) after opening the retroperitoneal space.

After removal of the sentinel node(s) a complete standard staging procedure will be performed including a comprehensive at random sampling of other lymph nodes at the different locations.

Surgical steps related to the study (standard or extra):

- Median laparotomy (standard care)
- Injection of blue dye and radioactive isotope (extra for the study)
- 15 minute waiting time during the surgery (extra for the study)
- Removal of the adnex and admittance to the pathologist for a frozen section analysis. (standard care)
- If the result is benign, no further actions will be performed in these patients and the procedure ends at this time. (standard care)
- If the result is malignant, the sentinel nodes will be identified either by the radioactive tracer and / or visually (blue dye). (extra for the study)
- The sentinel nodes will be removed. (standard or extra for the study, depending on whether or not the lymph node(s) would have been removed as part of the standard lymph node sampling)
- Subsequently a complete staging procedure will be performed. (standard care)

*Patients with endometrial cancer in whom a staging laparotomy is planned*

After making the median incision and opening the abdomen, blue dye and the radioactive isotope will be injected in the ligamentum ovarii proprium (median side) and the ligamentum infundibulo-pelvicum (lateral side) of one of the ovaries, in the same manner as described above in patients with a high suspicion of an ovarian malignancy. The choice of the ovary (left or right side) will switch between left and right by each patient who is included in the study.

A 15-minute interval will be planned after injection. In this time period at 5 and 10 minutes the radioactivity will be measured along the lymphatic tract to document whether or not perhaps sentinel node(s) can be identified at a shorter time-interval in future studies. The radioactivity is measured by a Geiger counter. The Geiger counter will be the same device in all surgeries.

After the 15 minutes time-interval the sentinel node(s) will be identified either (once more) by the radioactive tracer and / or visually (blue dye) after opening the retroperitoneal space.

After removal of the sentinel node(s) a complete standard staging procedure will be performed including a comprehensive at random sampling of other lymph nodes at the different locations.

Surgical steps related to the study (standard or extra):

- Median laparotomy (standard care)
- Injection of blue dye and radioactive isotope (extra for the study)
- 15 minute waiting time during the surgery (extra for the study)
- The sentinel nodes will be identified either by the radioactive tracer and / or visually (blue dye) (extra for the study)
- The sentinel nodes will be removed. (standard or extra for the study, depending on whether or not the lymph node(s) would have been removed as part of the standard lymph node sampling)
- Subsequently a complete standard staging procedure will proceed as normal (standard care).

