### Objective:

- 1) To determine whether or not a sentinel node procedure in patients with ovarian cancer is feasible when the tracers are injected in the ovarian ligaments.
- 2) To determine the anatomical localisations of the sentinel nodes.
- 3) To determine the incidence of false negative sentinel nodes.

**Study design:** phase I feasibility study.

**Study population:** the following patients will be included:

- Patients with a high suspicion of an ovarian malignancy in whom a median laparotomy and a frozen section analysis is planned.
- Patients with endometrial cancer in whom a staging laparotomy is planned.

**Intervention (if applicable):** After opening the abdomen, before starting the surgical staging procedure, blue dye and the radioactive-colloid will be injected in the ligamentum ovarium proprium and the ligamentum infundibulo-pelvicum. This will be done on the ovary with suspicion of malignancy (patients with an ovarian tumour) or one of the normal ovaries (patients with endometrial cancer).

**Main study parameters:** percentage of patients in whom it is feasible to identify sentinel nodes. Other study parameters are the anatomical localisation of the sentinel node(s) and the incidence of false negative lymph nodes.

**Nature and extent of the burden and risks associated with participation, benefit and group relatedness:** the surgery is prolonged with 20-25 minutes due to the required

incubation time after injection of the blue dye and radioactive isotope. A scintigram will be performed 24 hours after the surgery to determine whether residual radioactive lymph nodes

can be detected. The scintigram will only be performed if the patient is capable to be transported to the nuclear department. No extra blood samples will be taken, no extra visits, physical examinations or other tests are necessary. There is no risk of tumour dissemination by injecting the tracers in the ovarian ligaments. There is a 0,07 to 2,7% risk of an allergic reaction to the blue dye. The dose of radioactive isotope given does not give adverse side effects, either to the patients or the personnel present in the operating theatre.

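### Sentinel nodes are sought later, and after adnex removal, in ovarian than in endometrial patients, yet the detection rate, the interim rule and the node summary do not separate the two groups

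*Protocol*

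**What the plan says.** Under Surgical procedures (Section 5), the wait is the same in both groups: "A 15-minute interval will be planned after injection". So are the early readings: "At 5 and 10 minutes the radioactivity will be measured along the lymphatic tract", with one device used in all operations, to learn whether a shorter interval might do in later studies. No 15-minute reading is named.

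The next step differs. For endometrial patients: "After the 15 minutes time-interval the sentinel node(s) will be identified either (once more) by the radioactive tracer" or by blue dye, once the retroperitoneum is open. For patients with a suspicious ovary: "After the 15 minutes time-interval the adnex will be removed and admitted to the pathologist for a frozen section". Only after a malignant result is the retroperitoneum opened and the nodes sought.

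The ovarian subsection explains the wait as follows: "Common practice is to wait for 15 minutes, if in this time period the node is not detected, it is considered negative". It adds that the exact interval is not known and that a longer wait is impractical.

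The Summary defines the main parameter as "percentage of patients in whom it is feasible to identify sentinel nodes". The sample size section sets 20 evaluable patients of both tumour types, at least 10 with ovarian cancer. The 50% rule (Study design; Premature termination; Interim analysis) and the median and mean node number and main locations (Section 7) are given without a split by tumour type. Data collection (Section 5) records tumour type and the time from injection to detection.

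**The concern.** The protocol justifies including endometrial patients on the ground that they undergo the same operation (Primary Objective; Main study parameter). For the step that yields the endpoint, this is not so: the time since injection and the state of the injected side both differ by tumour type. A single percentage then averages two search conditions, while the primary objective asks about one of the two populations.

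Three things are at stake. A pooled rate could look acceptable while the ovarian rate is not, or the reverse. The decision at 10 procedures could depend on how many of the 10 happen to be ovarian. And in ovarian patients the early readings have nothing to be compared with at the end of the planned interval; the next documented look at the nodes comes after the adnex is out.

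**Working it through.** **Sequence, side by side**

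| Step | Endometrial | Ovarian |
|---|---|---|
| Readings at 5 and 10 min | yes | yes |
| Reading named at 15 min | no | no |
| Directly after 15 min | open retroperitoneum, search | remove adnex, frozen section |
| Search | then | after a malignant result, retroperitoneum opened |
| Adnex on injected side at search | no prior removal described | removed |

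**Elapsed time.** Let R be the time to open the retroperitoneum and X the time for adnex removal plus frozen section. Neither is in the protocol.

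- Endometrial search: 15 + R minutes after injection.
- Ovarian search: 15 + X + R minutes.
- Difference, taking R as similar in both: X, which is positive whatever its length.

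For an assumed X of 15 to 60 minutes and R = 0, the ovarian search falls at 30 to 75 minutes, that is 30/15 = 2 to 75/15 = 5 times the endometrial interval. Since R is above zero, the ratio (15 + R + X)/(15 + R) is smaller than that. Only the sign of the difference is established.

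**Group sizes.** The protocol plans 24 to 28 inclusions for 20 evaluable patients, with 60% of suspicious ovaries malignant on frozen section. With 10 ovarian cancers: 10/0.60 = 16.7, so 17, plus 10 endometrial = 27. With 12: 12/0.60 = 20, plus 8 = 28. Both lie in the stated range. Each group then has roughly 10 evaluable patients, so one patient moves a group's rate by about 1/10, or 10 percentage points.

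**What pooling could do (illustration only).** The protocol gives no expected detection rates, so all rates here are assumed. The interim rule is taken as stated under Study design and Premature termination: stop if fewer than 5 of 10 procedures identify a node. With m ovarian patients among the 10, the stopping probability is P(A + B < 5), where A ~ Bin(10 − m, endometrial rate) and B ~ Bin(m, ovarian rate).

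| Assumed rate, endometrial / ovarian | m = 0 | m = 5 | m = 10 |
|---|---|---|---|
| 40% / 40% | 63% | 63% | 63% |
| 40% / 60% | 63% | 37% | 17% |
| 40% / 80% | 63% | 14% | 0.6% |
| 50% / 90% | 38% | 2.8% | <0.1% |
| 70% / 90% | 4.7% | 0.5% | <0.1% |
| 80% / 40% | 0.6% | 14% | 63% |

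The last row is the third reversed, because the direction of any difference is also unknown. In that case the final pooled rate with 10 + 10 patients is (80% + 40%)/2 = 60%, above the 50% mark, while the ovarian rate is below it. If the rates are equal, the mix has no effect.

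**The case against.** Much can be said for the plan. Frozen section has to come first, because nodes are not resected in patients with a benign result; the ovarian sequence is the procedure under test. Tumour type and injection-to-detection time are already recorded, Section 7 lists its items per patient, and a split by tumour type is often left to the statistical analysis plan, which is not shown. All of this stands. It means that the surgical order is not at fault and that the split needs no new data. It does not settle which figure answers the primary objective, nor supply a 15-minute reading, which cannot be recovered after the operation.

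Stronger readings are tempting, and the protocol does not support them:

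- *That the groups share no reading under common conditions.* They share two, at 5 and 10 minutes, with the same device and before any adnex is removed.
- *That endometrial nodes are sought exactly at 15 minutes.* There too the retroperitoneum must be opened first, so a fixed multiple between the intervals cannot be claimed.
- *That a node found late counts as negative under a study rule.* The sentence describes common practice and explains the wait; it is not a scoring rule for this study. The wording is loose beside a later search, no more.
- *That a longer interval labels further nodes and so inflates the ovarian rate.* The protocol says nothing on this. Removal of the adnex might also limit further tracer entry, so elapsed time is not simply incubation time.
- *That the aim of the early readings cannot be met in ovarian patients.* That aim is only to document whether nodes might be identifiable sooner; a descriptive comparison with nodes found later remains possible.

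**Conclusion.** The point holds in a limited form. In ovarian patients the node search comes later than in endometrial patients by an unstated time, and after removal of the adnex beside the injection sites. The main percentage, the 50% rule and the node summary are nevertheless set without distinguishing the groups, although the objective concerns ovarian cancer. The early readings lack a 15-minute comparator before adnex removal in those patients.

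This affects every evaluable ovarian patient, at least 10 of 20. It rests on the written order of steps and on no assumed figure. The size and direction of any effect on detection are unknown; the interim probabilities show only that case mix could matter if the rates differ. Because time, tumour type and adnex removal go together, even a split by group cannot separate these causes. Which interval is right is not judged here.

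**What to change.** 1. In Section 7, and at the interim, report detection rate, number and location of sentinel nodes by tumour type alongside the pooled figure, each with the injection-to-detection time already collected.
2. In both surgical subsections, add a 15-minute reading along the lymphatic tract with the same device, before adnex removal or node search. Describe it as a comparator for the 5- and 10-minute readings. It should not replace the surgical detection result, since it involves no blue dye and no node removal.
3. Reconcile the sentence on nodes not found within 15 minutes with the later search in ovarian patients, and state which finding counts as detection for the main parameter.

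The planned wait and the order of surgery stay as written. The cost is one reading per patient, an added field on the data form and some protocol wording. The reading is probe-only with the retroperitoneum closed, and the per-group rates, on about 10 patients each, will be imprecise and should be presented as descriptive.

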### **After surgery**

One day after the surgery a scintigram will be taken if possible (depending on mobility of the patient) at the nuclear department to detect any remained radioactive hot spots. A scintigram is done in a similar way as a CT-scan. If there is any rest radioactivity this may indicate that

sentinel nodes have not been identified during surgery and therefore gives an indication of the reliability of identifying sentinel nodes during surgery.

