### ***Secondary study parameters***

In order to test the reliability of the sentinel node detection by injection in the ovarian ligaments, some secondary study parameters are also important:

- The anatomical location(s) and number of the sentinel node(s), visualized at surgery by either blue dye or the radioactive tracer
- The incidence of false negative lymph nodes, i.e. in contrast to the sentinel lymph node, one of the resected non-sentinel lymph nodes contains tumor cells. To calculate the percentage of false negative lymph nodes: the number of patients with negative sentinel lymph node(s) AND positive non-sentinel lymph node(s) is the numerator, the true amount of negative lymph nodes is the denominator."

The golden standard would be to perform a complete pelvic and para-aortic lymphadenectomy. However, the Dutch guideline advises a comprehensive lymph node sampling as standard treatment. We feel such a golden standard can be considered in subsequent study, when this study provides evidence that a sentinel node procedure in this way indeed is feasible. Nevertheless, a possible false negative result obtained in this study is important and therefore will be documented.

- The incidence of unrecognized sentinel nodes

Recognition of sentinel nodes with blue dye and the gamma probe during surgery is less reliable than by making a scintigram. Therefore ideally, as in breast and vulvar cancer, a scintigram is made before surgery to recognize the sentinel nodes so that during surgery no sentinel nodes will be missed. However, this principle cannot be accomplished in patients with ovarian cancer, because the tracers cannot be injected at the appropriate sides without opening the abdomen. However, we expect that missing sentinel nodes in patients with ovarian cancer occurs less frequent because the area where the sentinel nodes can reside is restricted to well described areas. Nevertheless, by making a scintigram 24 hours after surgery, at least an impression is obtained on the incidence of unrecognized sentinel lymph nodes.

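### A sentinel node missed in theatre but removed by the later node sampling never enters the count of unrecognised sentinel nodes

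*Protocol*

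**What the plan says.** Protocol section 5, Secondary study parameters, lists "The incidence of unrecognized sentinel nodes" as an outcome. The only measurement it names is the postoperative scan: "by making a scintigram 24 hours after surgery, at least an impression is obtained on the incidence of unrecognized sentinel lymph nodes". The After surgery section limits the target of that scan to what is still in the body, "to detect any remained radioactive hot spots", and makes the scan depend on whether the patient can be moved. It presents the result as an indication of how reliably sentinel nodes are identified during the operation.

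The order of events is set under Surgical procedures: "After removal of the sentinel node(s) a complete standard staging procedure will be performed including a comprehensive at random sampling of other lymph nodes". The same order holds for the endometrial cancer patients, and the scan follows a day later.

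For sampled nodes, section 7 (Descriptive statistics) registers number, location and metastasis. The Data collection list places its dye and gamma items among the sentinel-node items. For sampled tissue it asks for location and pathology only.

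A false negative is defined in Secondary study parameters as a negative sentinel node in a patient in whom "one of the resected non-sentinel lymph nodes contains tumor cells".

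**The concern.** The scan sees only what the surgeon left behind, and the surgeon removes more nodes between the sentinel step and the scan. A sentinel node that is overlooked and then taken in the sampling leaves a clean scan and a specimen labelled non-sentinel. The parameter meant to show how often recognition in theatre fails cannot register that kind of failure.

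The gap also blurs the reading of any false-negative case. If the positive sampled node was hot or blue, recognition failed, and technique might improve that. If it was cold and unstained, the drainage concept itself is in doubt for this injection route. The protocol says the route has, to its authors' knowledge, never been published, so the distinction is worth having. It can be made only on freshly excised tissue; no later analysis can recover it.

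**Working it through.** The protocol gives no figure for this parameter, so there is nothing to reproduce. The check traces the sequence and the records, then illustrates the size under stated assumptions.

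**1. Do sampled stations overlap with sentinel stations?** Yes. The Staging section names the para-aortic and paracaval region, the iliac vessels and the obturator fossa as the main areas to sample. The ten sentinel locations under Data collection cover para-aortic, interaortocaval, para-caval, common iliac, external iliac and obturator sites. The lists of surgical steps also accept the overlap: they class removal of a sentinel node as standard or extra according to whether the usual sampling would have taken it anyway.

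**2. Are missed sentinel nodes expected?** Yes, at some rate. Secondary study parameters states that recognition by dye and probe in theatre is less reliable than scintigraphy. It expects misses to be less frequent here than elsewhere, but not absent.

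**3. Does any record recover a missed node that was sampled?** No. The Data collection list includes an amount of gamma counts, but it stands with the sentinel-node items and is not assigned to sampled tissue.

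**4. Size of the lost component.** Let *u* be the true share of patients with one missed sentinel node, and *s* the chance that sampling removes that node. Suppose all 20 patients are scanned and the scan shows every hot node still in place. Then

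seen = 20 × u × (1 − s).

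The protocol gives neither *u* nor *s*; the ranges below are assumptions.

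| u | patients with a missed node | s = 0 | s = 25% | s = 50% | s = 75% |
|---|---|---|---|---|---|
| 10% | 2 | 2.0 | 1.5 | 1.0 | 0.5 |
| 20% | 4 | 4.0 | 3.0 | 2.0 | 1.0 |
| 30% | 6 | 6.0 | 4.5 | 3.0 | 1.5 |

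The proportional loss equals *s* whatever *u* is. That restates the assumption; it is not an estimate.

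**5. Net direction.** Let *f* be the share of patients whose only hot spot is something other than a missed sentinel node, for example activity at an injection site. The scan rate is then u(1 − s) + f, and its error is f − u × s. With u = 20% and s = 50%, u × s = 10%, so any *f* above 10% turns an understatement into an overstatement. The documents do not give *f*.

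**6. Link to false negatives.** At the cited 14.2% for clinical stage I–II ovarian cancer, 10 ovarian patients yield 10 × 0.142 = 1.42 node-positive patients. The chance of at least one is 1 − 0.858^10 = 78%, and of at least two 43%. For a missed node that is both sampled and metastatic, taking u = 20%, s = 50% and independence (all assumptions), the expected number is 10 × 0.20 × 0.50 × 0.142 = 0.14 patients. It would be 0.28 if all 20 had ovarian cancer. Both figures come before the further condition that the recognised sentinel node is negative. Such a case is unlikely, but with so few node-positive patients a single one would dominate the interpretation.

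**The case against.** The best defence is that the protocol claims little. It says that "at least an impression is obtained on the incidence of unrecognized sentinel lymph nodes", notes that residual activity only may point to a missed node, and leaves comparison against full lymphadenectomy to a later study. This is one descriptive secondary parameter in a 20-patient feasibility study, and the main parameter, the percentage of patients with an identified sentinel node, is unaffected. All of that stands and limits the weight of the point. It does not remove it: the modest wording nowhere tells the reader that hot nodes taken by sampling are outside what the scan can see.

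Three stronger readings are tempting, and the documents support none of them.

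- A reader might infer that the reported incidence is biased towards zero overall. Only one component is lost. Other residual activity can add to the count, and the balance is unknown.
- A reader might infer that a metastatic missed sentinel node is wrongly booked as a false negative. The protocol defines the term by what happened: recognised sentinel node negative, resected non-sentinel node positive. In such a patient the procedure gave the wrong answer, and counting it is correct. Restricting the term to cold nodes would flatter the rate.
- A reader might divide one such case by the handful of expected node-positive patients and report a very large swing in the false-negative proportion. The protocol states a different denominator, based on true negatives. If that is read as node-negative patients, one case is 1/(10 × 0.858) = 1/8.58, about 12 points, or 1/(20 × 0.858) = 1/17.16, about 6 points.

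**Conclusion.** The point holds for the measurement of unrecognised sentinel nodes. As written, a node missed at the sentinel step and then removed by sampling cannot be counted. This follows from the order of procedures and the list of recorded items, and needs no assumption about rates. The size of the loss does need one: it equals the share of missed nodes that sampling removes, and the documents do not give that share. Because sampling is described as "including a comprehensive at random sampling of other lymph nodes at the different locations" and is not a complete lymphadenectomy, no particular value can be defended.

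The false-negative numerator is sound and should stay. What is missing there is only the information to tell a detection miss from a failure of the sentinel concept. Overall this is a cheap improvement to a secondary parameter, worth making because the data are otherwise lost for good. It does not threaten the study's main result.

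**What to change.** 1. **Measure.** Before sampled tissue goes to pathology, pass the counter already used in theatre over it, station by station, and inspect it for blue dye. Fix the count threshold for calling tissue hot before the first patient; the protocol gives no value to borrow.
2. **Record.** Add hot/cold and blue/not blue by station to the existing form, where the location of sampled tissue is already entered.
3. **Report.** Give the number of patients with a hot or blue sampled node next to the number with a residual hot spot on the scan, each over its own denominator, since not every patient will be scanned. Call both possible unrecognised sentinel nodes.
4. **False negatives.** Keep the present numerator unchanged. Add a descriptive split by whether the positive non-sentinel node was hot or blue, or cold and unstained, with the total always shown.

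The cost is one form entry per station and perhaps a few extra minutes of counting on tissue already excised. The time is an assumption; the documents give no figure. Nothing further is done to the patient. One limit remains and should be stated in the report: a hot sampled node may be a later-draining node rather than a true sentinel node, so the new count has its own upward error.
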